#### 4.3.2. Sample Size Re-estimation

The sample size will not be re-estimated based on the results of the 1st interim analysis.

The 2nd interim analysis will be triggered 24 weeks after at least one-third of patients required to be enrolled are randomized, and will be based on the data from all patients who are expected to complete 24 weeks of treatment. The sample size may be re-estimated based on the 2nd interim analysis results being reviewed by the DMC. For the primary endpoint, if futility criterion is not met (see [Section 5.1](#) for the futility criterion) and the conditional power under the current trend at the time of the interim look is within the pre-specified promising zone from 0.40 to 0.90, the DMC may recommend increasing the sample size by a pre-specified fixed number of 150 to ensure sufficient power. This method is referred to as the CDL adaptive method and was initially proposed by Chen, DeMets, and Lan (2004) as later extended by Gao, Ware and Mehta (2008) and Mehta and Pocock (2011) ([Chen 2004](#); [Gao 2008](#); [Mehta 2011](#), respectively). It is used to control type-1 error for sample size increase based on unblinded interim data. Within the pre-specified promising zone and a pre-specified fixed increase of the sample size, the CDL method could allow the final analysis to include all data before and after the interim look without inflating the type-1 error.

### 4.4. Randomization

Eligible ALS patients will be randomized in a 2:1 ratio to receive 300 mg reldesemtiv twice daily or placebo twice daily, respectively, for the first 24 weeks (double-blind, placebo-controlled period). The stratification factors for randomization are baseline riluzole use and baseline edaravone use.

## **4.5. Clinical Assessments**

### **4.5.1. Efficacy Assessments**

Efficacy assessments include Amyotrophic Lateral Sclerosis Functional Rating Scale-Revised (ALSFRS-R), forced vital capacity (FVC), handgrip strength and muscle strength. Additionally, Milano-Torino staging (MiToS) will be derived based on the ALSFRS-R item scores.

#### **4.5.1.1. Amyotrophic Lateral Sclerosis Functional Rating Scale-Revised (ALSFRS-R)**

The Amyotrophic Lateral Sclerosis Functional Rating Scale-Revised (ALSFRS-R) is a validated rating instrument for monitoring the progression of disability in patients with ALS ([Cedarbaum 1999](#)). The assessment is based on 12 clinical ratings that are categorized in four domains: bulbar (speech, salivation, swallowing), fine motor skills (handwriting, cutting food and handling utensils, dressing hygiene), gross motor skills (turning in bed and adjusting bedclothes, walking, climbing stairs) and respiratory function (dyspnea, orthopnea, respiratory insufficiency). Each clinical rating is assessed using an ordinal scale that ranges from 0 to 4, with a score of 4 representing normal function and lower scores indicating worse function.

The score of each of the four domains (bulbar, fine motor skill, gross motor skill, and respiratory function) is calculated as the sum of the three ratings within each domain and can range from 0 to 12. If a single rating is missing, the score of the corresponding domain will be set to missing.

The ALSFRS-R total score is calculated as the sum of the 12 ratings and can range from 0 to 48 with higher scores indicating less functional impairment. If a single rating is missing, the ALSFRS-R total score will be set to missing.

The score change from baseline will be calculated as the post baseline score minus the baseline score, so that a negative number for change from baseline indicates greater impairment relative to baseline. A positive treatment difference in the change from baseline (reldesemtiv minus placebo) favors reldesemtiv.

#### **4.5.1.2. Percent Predicted Force Vital Capacity (Percent Predicted FVC)**

The forced vital capacity (FVC) measures the amount of air a person can forcefully and quickly exhale after inhaling as deeply as possible. FVC measurements will be collected in clinic and remotely. The patient will perform the maneuver 3 times; up to 5 measurements will be taken if the variability of the two highest measurements is  $\geq 10\%$ . Variability is calculated as (highest FVC measurement - 2nd highest FVC measurement) / highest FVC measurement. FVC tracings for this study will be reviewed centrally by independent pulmonologists. Volume time curves will be reviewed for acceptability guided by criteria from the American Thoracic Society and the European Respiratory Society (American Journal of Respiratory and Critical Care Medicine 2019; Vol 200, Number 8). Tracings with variability  $\geq 10\%$  between the 2 highest values are not acceptable. Those tracings that are viewed as acceptable will be 'evaluable' and will be included in the analysis. Furthermore, among FVC measurements collected during a visit, the highest result of the evaluable measurements will be used for analysis as long as the pulmonologist has confirmed it is acceptable. FVC measurements collected in clinic and remotely may be combined for analysis if a systematic difference across the entire study population is not observed; otherwise, they will be analyzed separately given that some clinic sites may only collect FVC data remotely during the COVID-19 pandemic due to safety and local health regulations. The

evaluation of whether the systematic difference exists will be performed before the database lock.

The percent predicted FVC represents the FVC measurement as a percent of the predicted values based on sex, age, height, and race. It is calculated as: Percent Predicted FVC = (Trial FVC / Predicted FVC) x 100 (%).

The predicted FVC is calculated using the Quanjer GLI-2012 Regression Equation ([Quanjer 2012](#)) that factor the characteristics of sex, age, height and race into the prediction.

For males,

$$\text{Predicted FVC} = \exp [ -11.2281 + 2.4135 \times \ln(\text{Height})(\text{cm}) + 0.0865 \times \ln(\text{Age})(\text{yrs}) - 0.1684 \times \text{AfrAm} - 0.0405 \times \text{NEAsia} - 0.1177 \times \text{SEAsia} - 0.0825 \times \text{Other} + \text{Mspline}]$$

For females,

$$\text{Predicted FVC} = \exp [ -10.403 + 2.2633 \times \ln(\text{Height})(\text{cm}) + 0.0234 \times \ln(\text{Age})(\text{yrs}) - 0.1555 \times \text{AfrAm} - 0.0262 \times \text{NEAsia} - 0.1516 \times \text{SEAsia} - 0.0833 \times \text{Other} + \text{Mspline}]$$

where

$\ln( )$  = natural log transformation

AfrAm = 1 if a patient is African American; otherwise = 0

NEAsia = 1 if a patient is from North East Asia; otherwise = 0

SEAsia = 1 if a patient is from South East Asia; otherwise = 0

Other = 1 if a patient belongs to other ethnic group except for Caucasian, or has mixed race/ethnicity; otherwise = 0

(See <https://www.ers-education.org/guidelines/global-lung-function-initiative/faq/what-reference-equations-do-i-apply-for-non-caucasians/> for the definitions of regions used in the Quanjer GLI-2012 Regression Equation.)

Mspline is determined by age and sex as shown in [Section 12.4](#).

Generally, the percent predicted FVC declines over time in patients with ALS. The change from baseline in percent predicted FVC will be calculated as the post baseline value minus the baseline value, so that a negative number for change from baseline indicates respiratory function decline relative to baseline, and a positive treatment difference (reldeemtiv minus placebo) favors reldeemtiv.

#### 4.5.1.3. Milano-Torino Staging (MiToS)

Milano-Torino staging (MiToS) was developed to measure loss of independence in the 4 key domains on ALSFRS ([Chio 2015](#)): movement (walking/self-care), swallowing, communicating and breathing. Each MiToS domain score is derived from related ALSFRS-R item scores as shown in [Table 1](#). The sum of the 4 MiToS domain scores has a range from 0 to 4 that corresponds to MiToS Stage 0, Stage 1, Stage 2, Stage 3 and Stage 4, where Stage 0 represents possible functional involvement but no loss of independence on any domain, and Stages 1 to 4 represent number of domains in which independence was lost. In addition, MiToS Stage 5 represents death.

**Table 1: MiToS Domain Scores Mapping from ALSFRS-R Item Scores**

Domain	ALSFRS-R Items Used for Mapping	Mapping Algorithms
Movement (walking/self-care)	Q8: Walking 4=Normal 3=Early ambulation difficulties 2=Walks with assistance 1= Non-ambulatory functional moment only 0= No purposeful leg movement	If Q8 or Q6 has an item score=0 or 1 then MiToS movement domain score=1; else MiToS movement domain score=0
	Q6: Dressing and hygiene 4= Normal function 3= Independent and complete self-care with effort or decreased efficiency 2= Intermittent assistance or substitute methods 1= Needs attendant for self-care 0= Total dependence	
Swallowing	Q3: Swallowing 4= Normal eating habits 3= Early eating problems; occasional choking 2= Dietary consistency changes 1= Needs supplemental tube feeding 0= NPO (exclusively parenteral or enteral feeding)	If Q3 has an item score=0 or 1 then MiToS swallowing domain score=1; else MiToS swallowing domain score=0
Communicating	Q1: Speech 4= Normal speech processes 3= Detectable speech with disturbances 2= Intelligible with repeating 1= Speech combined with non-vocal communication 0= Loss of useful speech	If both Q1 and Q4 have items scores= 0 or 1 then MiToS communicating domain score=1; else MiToS communicating domain score=0.
	Q4: Handwriting 4= Normal 3= Slow or sloppy; all words are legible 2= Not all words are legible 1= Able to grip pen but unable to write 0= Unable to grip pen	
Breathing	Q10: Dyspnea 4= None 3= Occurs when walking 2= Occurs when one or more of: eating, bathing, dressing 1= Occurs at rest, difficulty breathing when either sitting or lying 0= Significant difficult, considering using mechanical respiratory support	If Q10 has an item score=0 or 1 or Q12 has an item score=0, 1 or 2 then MiToS breathing domain score=1; else MiToS breathing domain score=0
	Q12: Respiratory insufficiency 4= None 3= Intermittent use of NIPPV 2= Continuous use of NIPPV during the night 1= Continuous use of NIPPV during the night and day 0= Invasive mechanical ventilation by intubation or tracheostomy	

#### 4.5.1.4. Handgrip Strength

Handgrip strength will be measured bilaterally by an electronic hand dynamometer with grip extenders to be attached to the front and/or back handle as needed dependent upon patient's hand size. The width of the grip (with no extender, 1 grip extender or 2 grip extenders) will be used consistently throughout the study. Patients will be asked to squeeze the device with the maximum possible force for a short interval to establish the maximum voluntary contraction. The greater of the two maximum handgrip strength attempts for each hand will be used. The secondary endpoint, change from baseline to Week 24 in handgrip strength, will be analyzed using the average grip strength of both hands.

#### 4.5.1.5. Muscle Strength

Patients' muscle strength will be measured bilaterally using hand held dynamometry (HHD). The HHD testing will measure muscle strength of three intrinsic hand muscle groups tested bilaterally: abductor pollicis brevis, first dorsal interosseous, and abductor digiti minimi. Two measurements will be obtained for each muscle tested. If the 2 measurements have a variability  $> 0.15$  then a 3rd test will be performed. The variability is calculated as:  $(\text{Max Value} - \text{Min Value}) / \text{Max Value}$ . The maximum result of the 2 or 3 measurements obtained will be used for analysis.

The muscle strength will be recorded as 0 (pounds) on the electronic case report form (eCRF) for the following situations:

- A patient is able to assume the correct position but unable to exert any force.
- A patient is unable to assume the correct position, and the evaluator is able to determine the cause as muscle weakness or contracture.

The muscle strength of each measured body location will be transformed as a percent change from baseline using the equation:  $[(\text{post baseline value} - \text{baseline value}) / \text{baseline value}] \times 100$ . The transformed muscle strength will be set to missing if the baseline value is zero.

The mega score is a composite score that averages strength across muscle groups. It is calculated as the mean of the non-missing transformed muscle strength scores among the three muscle groups of the hands measured bilaterally by the HHD.

A greater muscle strength mega score indicates less muscle strength loss, and a positive treatment difference (reldesemtiv minus placebo) favors reldesemtiv.

#### 4.5.2. Safety Assessments

Safety assessments include adverse events and serious adverse events, Beck Depression Inventory-Fast Screen (BDI-Fast Screen), electrocardiograms, laboratory assessments, neurological examinations, physical examinations and vital signs.

##### 4.5.2.1. Beck Depression Inventory (BDI)

The Beck Depression Inventory (BDI®) — Fast Screen (BDI-FS) is a shortened version of the BDI-II that evaluates key symptoms of depression. It was developed to factor out co-occurring depression symptomatology that may be related to a medical condition (Steer 1999), and concentrate on factors of depression that relate solely to depression. The BDI-FS contains 7 self-

reported items that evaluate major depressive symptoms over the past 2 weeks, including sadness, pessimism, past failure, loss of pleasure, self-dislike, self-criticalness, and suicidal ideations (Beck 2000; Steer 1999). Individual scale items are scored on a 4-point continuum (0=least, 3=most). The total score is calculated as the sum of the scores from the 7 items and can range from 0 to 21. Higher scores indicate greater depressive severity. Patient’s depression level will be classified using the BDI total score as shown in Table 2. The BDI total score will be set to missing if an answer to any of the 7 items is missing.

**Table 2: Depression Level Classification by BDI Total Score**

Depression Level	BDI Total Score
Minimal Depression	0 – 3
Mild Depression	4 – 6
Moderate Depression	7 – 9
Severe Depression	10 – 21

#### 4.5.3. Pharmacokinetic Assessments

Single blood samples will be collected to evaluate plasma concentrations of reldesemtiv and its metabolite, CK-2127106 at Weeks 4, 12 and 24. An optional intensive PK substudy will be conducted at Week 36. Pharmacokinetic (PK) parameters, such as trough concentration ( $C_{trough}$ ), maximum observed concentration ( $C_{max}$ ),  $T_{max}$ ,  $AUC_{tau}$ ,  $AUC_{last}$  and CL/F (reldesemtiv only) and metabolite ratio, if available, will be calculated.

#### 4.5.4. Health Economic Outcome Measures and Quality of Life Assessments

##### 4.5.4.1. EQ-5D-5L and EQ-VAS

The instrument EQ-5D is a standardized measure of health status for clinical and economic appraisal (EuroQol Group 1990), which consists of two parts: a short descriptive system questionnaire (EQ-5D-3L) and a visual analogue scale (EQ-VAS).

EQ-5D-5L is the 5-level version of EQ-5D introduced to improve the instrument’s sensitivity and to reduce ceiling effects (EuroQol Group 2009). The descriptive system comprises 5 dimensions: mobility, self-care, usual activities, pain/discomfort and anxiety/depression. Each dimension has 5 levels indicating no problems, slight problems, moderate problems, severe problems or extreme problems. Five responses with a response from each of the 5 dimensions form a 5-digit number that defines a patient’s health state profile. A health state can potentially be assigned a summary index score based on societal preference weights (societal perspective) for the health state. The health state preferences often represent national or regional values and can therefore differ between countries/regions. The health state index scores will be calculated using the composite time trade-off (cTTO) method based on the United States valuation of EQ-5D-5L (Pickard 2019) for patients from the United States and for the FAS. The health state index score ranges from less than 0 to 1 with higher scores indicating higher health utility; a score 0 represents death, negative values represent worse than death, and 1 represents full health.

EQ-VAS rates a patient’s perceived health on a vertical visual analogue scale from 0 to 100, where 0 represents the worst imaginable health and 100 represents the best imaginable health. The VAS can be used as a quantitative measure of health outcome that reflects the patient’s own judgement.

**4.5.4.2. Use of Durable Medical Equipment (DME)**

At screening and on Day 1, patients will be asked if they have any of the listed durable medical equipment (DME) (manual wheelchair, power wheelchair, non-invasive ventilation (NIV), gastrostomy tube, augmentative and alternative communication) and if so, the extent of current DME use (has obtained but not using, first use, daily use or dependent) as defined in Table 3, or patient stopped using and the reason of stopping using (as applicable). In the subsequent visits that collect the DME assessments, patients will be asked if any of the listed DME has been prescribed for them and they have agreed to it since the last visit. And if yes, the date of prescription. Patients will also be asked for the extent of current DME use or if they have changed their extent of DME use since the last visit.

**Table 3: Definitions of Receipt, First Use, Daily Use and Dependent of the Durable Medical Equipment**

Category	Durable Medical Equipment				
	Manual Wheelchair	Power Wheelchair	Non-invasive Ventilation	Gastrostomy	Augmentative and Alternative Communication
Receipt	Has received (either through insurance or other source)	Has received (either through insurance or other source)	Has received	Has received	Has received (either through insurance or other source)
First use	Use for any reason and in any location	Use for any reason and in any location	Any use outside of being instructed on how to use it – can be day or night use	Any use outside of being instructed on how to use it or flushing it – can be for the purposes of administering medicines, free water, nutrition	Any use for the purposes of communication outside of being instructed on how to use device
Daily use	Daily use (any duration)	Daily use (any duration)	Daily use (can be day or night use) for 4 or more total hrs/24 hrs	Daily use for replacing or supplementing one or more meals per day	Daily use for the purposes of communication
Dependent	Non-ambulatory, wheelchair dependent	Non-ambulatory, wheelchair dependent	Use 22 or more hrs/day	Use for essentially all nutrition, may still take food by mouth for pleasure	Use for all communication

#### **4.5.4.3. Amyotrophic Lateral Sclerosis Assessment Questionnaire (ALSAQ-40)**

The Amyotrophic Lateral Sclerosis Assessment Questionnaire (ALSAQ-40) is a 40-item questionnaire that was created specifically to assess health-related quality of life in patients with ALS. ALSAQ-40 includes 40 items for the 5 domains: physical mobility (10 items), activities of daily living and independence (10 items), eating and drinking (3 items), communication (7 items) and emotional reactions (10 items). Based on a two-week recall of experiences patients may have had, each item is rated by frequency of occurrence on a five-point Likert scale (1 = never, 2 = rarely, 3 = sometimes, 4 = often, 5 = always or cannot do at all). For each domain, the sum of scores from all items of a domain is then converted to a summary score from 0 (best health status) to 100 (worst health status) using the equation: (sum of all non-missing item scores / maximum possible sum of all non-missing item scores) x 100. The ALSAQ-40 total score is calculated as the sum of the summary scores from the 5 domains. A lower score corresponds to better health-related quality of life.

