##### **3.2.2. Secondary Endpoints**

- Combined assessment of change in ALSFRS-R total score, time to dependence on assisted ventilation and survival time up to Week 24. Dependence on assisted ventilation is defined as using non-invasive or invasive ventilation for  $\geq 22$  hours per day for  $\geq 10$  consecutive days.
- Change from baseline to Week 24 in the percent predicted forced vital capacity (FVC)
- Change from baseline to Week 24 in the ALSAQ-40 total score
- Change from baseline to Week 24 in handgrip strength (average of both hands)

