## 8.5. Multiple Comparisons and Multiplicity

The null hypothesis for the primary and secondary efficacy endpoints will be tested in a prespecified order using a closed testing procedure. This procedure will maintain the family-wise error rate at two-sided significance level of 0.0499 for all primary and secondary hypotheses tested in a confirmatory sense. The testing steps are described as follows:

- Step 1: The null hypothesis for the primary endpoint  $H_{01}$  is that there is no treatment difference in the change from baseline to Week 24 in ALSFRS-R total score between patients randomized to placebo and those randomized to reldesemtiv in the FAS. The hypothesis will be tested at the two-sided significance level of 0.0499. If this hypothesis is rejected, testing will proceed to Step 2; otherwise testing will stop.
- Step 2: The null hypotheses for the first secondary endpoint  $H_{02}$  is that the Mann-Whitney probability of a more favorable status in reldesemtiv or placebo group in the FAS is 0.5. The status is quantified by joint ranks based on the combined assessment of change in ALSFRS-R total score, time to onset of respiratory insufficiency, and survival time up to Week 24. The hypotheses will be tested at the two-sided significance level of 0.05. If this hypothesis is rejected, testing will proceed to Step 3; otherwise testing will stop.
- Step 3: The null hypotheses  $H_{03}$  is that there is no treatment difference in change from baseline to Week 24 in the percent predicted FVC between patients randomized to placebo and those randomized to reldesemtiv in the FAS. The hypotheses will be tested at the two-sided significance level of 0.05. If this hypothesis is rejected, testing will proceed to Step 4; otherwise testing will stop.
- Step 4: The null hypotheses  $H_{04}$  is that there is no treatment difference in change from baseline to Week 24 in the ALSAQ-40 total score between patients randomized to placebo and those randomized to reldesemtiv in the FAS. The hypotheses will be tested at the two-sided significance level of 0.05. If this hypothesis is rejected, testing will proceed to Step 5; otherwise testing will stop.

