- Combined assessment of change in the percent predicted FVC, time to dependence on assisted ventilation (either invasive or non-invasive), and survival time up to Week 24
- Combined assessment of change in the ALSAQ-40 total score, time to dependence on assisted ventilation (either invasive or non-invasive), and survival time up to Week 24
- Change from baseline to Week 24 in FVC (liters)
- Change from baseline to Week 48 in percent predicted FVC
- Slope of change from baseline to Week 24 in percent predicted FVC
- Changes from baseline to Week 24 and Week 48 in forced expiratory volume in the first second
- Change from baseline to Week 24 and Week 48 in percent predicted FVC measured remotely
- Change from baseline to Week 48 in the ALSAQ-40 total score
- Changes from baseline to Week 24 and Week 48 in the subscores of ALSAQ-40
- Time to event for the first intrinsic hand muscle reaches zero from baseline to Week 24 and Week 48
- Time to event for all intrinsic hand muscles reach 0 from baseline to Week 24 and Week 48
- Progression in the degree use of both new and pre-existing DMEs from baseline up to Week 48

The following analyses will also be conducted if a systematic difference between in clinic measurements (from the Easy One spirometers) and remote measurements (from the NuvoAir spirometers) is not observed:

- Change from baseline to Week 24 and Week 48 in percent predicted FVC, with remote measurements collected in the same analysis windows as those used to substitute for the missing in clinic measurements.
- Change from baseline to Week 24 and Week 48 in percent predicted FVC measured in clinic and remotely. In clinic measurements take precedence if both in clinic and remote measurements are collected in the same analysis window.

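### The ALSAQ-40 conversion formula, applied to items scored 1 to 5, gives domain scores of 20 to 100 rather than the stated 0 to 100, so differences come out at 0.8 of the stated scale

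*SAP*

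**What the plan says.** The only ALSAQ-40 scoring rule in the two documents is in SAP Section 4.5.4.3. It contains four relevant elements.

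- Item coding: "1 = never, 2 = rarely, 3 = sometimes, 4 = often, 5 = always or cannot do at all".
- Domain sizes: "physical mobility (10 items), activities of daily living and independence (10 items), eating and drinking (3 items), communication (7 items", plus emotional reactions with 10 items, 40 in all.
- Target scale: each domain sum is "converted to a summary score from 0 (best health status) to 100 (worst health status".
- Equation: "sum of all non-missing item scores / maximum possible sum of all non-missing item scores) x 100".

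The total is then built from the domains: "The ALSAQ-40 total score is calculated as the sum of the summary scores from the 5 domains".

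The score is used in several places. SAP Section 3.2.2 lists "Change from baseline to Week 24 in the ALSAQ-40 total score" as a secondary endpoint. SAP Section 8.5 tests it at Step 4 of the fixed sequence, with the null hypothesis of "no treatment difference in change from baseline to Week 24 in the ALSAQ-40 total score". SAP Section 8.8 adds "Changes from baseline to Week 24 and Week 48 in the subscores of ALSAQ-40", the Week 48 change in the total, and a joint-rank analysis that includes the total. SAP Section 7.11 calls for baseline summaries, and SAP Section 6.1 calls for least squares means, differences, standard errors and 95% confidence intervals from the models.

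**The concern.** Dividing a sum by its maximum gives a score that starts at 0 only if the smallest possible sum is 0. With items starting at 1 it is not, so the printed equation cannot deliver the range stated in the same sentence.

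The stake is the reported estimate. A reader told that 0 is the best status would see a patient with no reported problems score 20 in each domain and 100 in total. The Week 24 difference and its interval would be in units smaller than the ones described, which matters for judging clinical relevance and for comparison with results on a true 0 to 100 scale. Two programmers, one following the stated range and one following the equation, would produce different tables from the same data.

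**Working it through.** **Inputs** (all from SAP Section 4.5.4.3): item minimum 1 and maximum 5; domain sizes k = 10, 10, 3, 7, 10; stated domain range 0 to 100; total = sum of five domain scores.

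**Step 1: try to reproduce the stated range.** With S the sum over k answered items, the equation as written is

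score = 100 × S / (5k).

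| Domain | k | Lowest S | Highest S | Lowest score | Highest score |
|---|---|---|---|---|---|
| Physical mobility | 10 | 10 | 50 | 10/50 × 100 = 20 | 100 |
| Daily living and independence | 10 | 10 | 50 | 10/50 × 100 = 20 | 100 |
| Eating and drinking | 3 | 3 | 15 | 3/15 × 100 = 20 | 100 |
| Communication | 7 | 7 | 35 | 7/35 × 100 = 20 | 100 |
| Emotional reactions | 10 | 10 | 50 | 10/50 × 100 = 20 | 100 |

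The stated range is not reproduced. Each domain spans 80 points, not 100. The total runs from 5 × 20 = 100 to 5 × 100 = 500, a span of 400. The SAP prints no range for the total, but five domains of 0 to 100 imply 0 to 500.

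**Step 2: look for a reading that does give 0 to 100.**

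- Items 1 to 5, divided by 4k without subtracting the minimum: 25 to 125. No.
- Items recoded 0 to 4, then 100 × S / (4k): 0 to 100. Yes, but the SAP states 1 to 5 and no recoding.
- Items 1 to 5, 100 × (S − k) / (4k): 0 to 100. Yes, but this is not the printed equation.

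**Step 3: relate the two scales.** Let m = S/k be the mean answered item.

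- As written: 100 × S / (5k) = 20m.
- True 0 to 100: 100 × (S − k) / (4k) = 25(m − 1).

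Substituting m = 1 + (true score)/25 gives

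score as written = 20 + 0.8 × (true score).

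The constant cancels in any change or difference, leaving a factor of exactly 0.8. For the total, score as written = 100 + 0.8 × (true total). One raw item point is worth 2.00, 2.86 or 6.67 as written (10, 7 or 3 items), against 2.50, 3.57 or 8.33 on the true scale; each ratio is 0.8. A 10-point difference in the total becomes 0.8 × 10 = 8.

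**Step 4: missing items.** The relation depends only on m, so it holds when items are missing. In 20,000 random pairs of domain scores with random missing items, every ratio of differences with a non-zero denominator was 0.8.

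**Step 5: effect on testing.** In a simulated two-group example with 185 and 370 patients, the difference in totals was −10.58 as written and −13.23 on the true scale (ratio 0.8), and t was −6.573 on both. A linear rescaling with positive slope also leaves joint-rank orderings unchanged.

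**The case against.** The best case on the other side is that the text does not show which of its three elements is the slip. If the database or programs hold items as 0 to 4, the printed equation gives exactly 0 to 100 and no reported number would be wrong. The case report form and derivation specifications are not in the two documents, and Protocol Section 8.1.6 sends the reader to the Study Manual. The factor of 0.8 therefore applies if the SAP is programmed as written. That condition is fair, but it does not rescue the text: the SAP prints 1 to 5 coding, nothing else in either document recodes the items, and the sample code in SAP Section 12.5 does not derive the score.

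It is also true that nothing else in the plan depends on the absolute scale. There is no responder threshold, minimal important difference, power calculation or interim boundary in ALSAQ-40 points; the sample size rests on ALSFRS-R. The mixed model in SAP Section 8.7.3 lists baseline ALSFRS-R, not baseline ALSAQ-40, as its baseline covariate. All five domains shrink by the same factor, so their relative weight in the total is unchanged. A standardised effect is unchanged too, because the standard error shrinks with the estimate; only the raw-unit effect is smaller. All of this stands, and it limits the point to reporting.

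**Conclusion.** The concern holds. As written, with items 1 to 5 and the printed equation, each domain runs from 20 to 100 and the total from 100 to 500, and the stated best score of 0 cannot occur. Means are shifted and compressed; changes, differences, standard errors and confidence limits are exactly 0.8 of their values on the stated scale. This is exact and needs no outside figure. It rests on one assumption: that the derivation is programmed as the SAP describes it.

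No hypothesis test, p-value, ranking or step in the testing sequence changes. The point should still be corrected, because the score is a confirmatory secondary endpoint whose estimate and interval will be reported in points, but it is not a threat to the trial's inference.

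**What to change.** In SAP Section 4.5.4.3, replace the equation for each domain with

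100 × (sum of answered items − number of answered items) / (4 × number of answered items),

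or keep the equation and state that items are recoded from 1–5 to 0–4 before it is applied, so that the maximum is 4 per item. Either gives 0 to 100 per domain. Also state that the total runs from 0 to 500, and check that the derivation program and table footnotes agree with the text.

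The cost is one line of SAP text and one derivation, with no change to data collection. It should be made before database lock, when SAP Section 2 says analysis decisions are to be settled. If the programs already use 0 to 4 coding, the text still needs correcting; SAP Section 6.4 requires differences in data handling to be documented, so a silent programming correction is not enough.
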